- 3.1.7 The effects of LY3214996 or HCQ on the developing human fetus are unknown. For this reason and because anti-cancer agents are known to be teratogenic, women of child-bearing potential and men must agree to use adequate contraception (hormonal or barrier method of birth control; abstinence) prior to study entry and for the duration of study participation. Should a woman become pregnant or suspect she is pregnant while she or her partner is participating in this study, she should inform her treating physician immediately. Men treated or enrolled on this protocol must also agree to use adequate contraception prior to the study, for the duration of study participation, and 6 months after completion of LY3214996 or HCQ administration.
- 3.1.8 Ability to understand and the willingness to sign a written informed consent document.
- 3.1.9 Ability to swallow and retain oral medication.
- 3.1.10 Baseline QTcB of  $\leq 470$  msec on screening EKG.
- 3.1.11 Participants must be able and willing to undergo the pre-treatment biopsy procedure, and have a cancer site amenable to biopsy.

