#### 5.1.4 Treatment Cross-Over

Participants who are enrolled to **Arm 2** who experience radiologic disease progression on monotherapy will have the option to cross-over to receive treatment with the combination. Cross-over will occur at the treating investigator's discretion following consultation and approval from the overall principal investigator. Participants who cross-over must meet all of the following criteria:

1. The participant does not meet any other investigational product discontinuation criteria (see **Section 5.5**).
2. ECOG performance status is  $\leq 1$ .
3. Absence of rapid disease progression or threat to vital organs/critical anatomical sites (e.g. spinal cord compression) requiring urgent alternative medical intervention.
4. The participant must have a tumor imaging assessment and EKG prior to initiating cross-over treatment (within 28 days of the start of combination dosing). All subsequent assessments will continue with the same frequency defined in the **Study Calendar** and **Section 11**.

5. Participants must re-consent prior to treatment cross-over.

The treating investigator should ensure that patients do not have any significant, unacceptable, or irreversible toxicities indicating that continuing treatment will not benefit the patient.

Participants should be made aware of the potential risks of initiating combination therapy by the treating investigator and must provide re-consent prior to the beginning of cross-over therapy.

Participants who cross-over will receive LY3214996 and HCQ at the dose being administered to **Arm 1** participants. Under no circumstances may a participant crossing-over receive treatment with HCQ at a dose level higher than what is being evaluated on **Arm 1**. Participants enrolled to **Arm 2** who cross-over will not be considered one of the six required participants for the safety analysis of **Arm 1** (see **Section 5.1.3.1**). In the event combination dosing was not found tolerable during the safety lead-in, no treatment with HCQ will be permitted.

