### 6.3        Toxicity Management Guidelines

Management of toxicity considered *at least possibly related* to HCQ and/or LY3214996 is detailed in the tables below.

| Table 7: Hematologic Toxicity Management |             |  |
|--|-------------|--|
| Event Terms                              | CTCAE Grade | Management Guidelines  |
| Neutrophil count decreased               | ≥ Grade 3   | Hold study agent(s) until recovery to ≤ Grade 2, resume with one dose level reduction. |
| Febrile neutropenia                      | ≥ Grade 3   | Hold study agent(s) until resolution, resume with one dose level reduction.            |
| Platelet count decreased                 | ≥ Grade 3   | Hold study agent(s) until recovery to ≤ Grade 2, resume with one dose level reduction. |

| Table 8: Non-Hematologic Toxicity Management |             |   |
|--|-------------|---|
| Event Terms                                  | CTCAE Grade | Management Guidelines   |
| Ocular Toxicity                              | ≤ Grade 2   | 
Ocular toxicity is associated with HCQ, and blurred vision has been observed in patients receiving LY3214996.
 
Participants experiencing new or worsening visual disturbances or suspected ocular toxicity of any grade while receiving study treatment should be referred for ophthalmic examination.
 
In the case of mild or moderate ocular toxicity (i.e. CTCAE Grade 1 or Grade 2), the treating investigator may hold and/or dose reduce the study agent(s) at their discretion.
 |
| Ocular Toxicity                              | ≥ Grade 3   | 
Ocular toxicity is associated with HCQ, and blurred vision has been observed in patients receiving LY3214996.
 
Participants experiencing new or worsening visual disturbances or suspected ocular toxicity of any grade while receiving study treatment should be referred for ophthalmic examination.
 
Hold study agent dosing until resolution to ≤ Grade 2 or baseline. Resume with one dose level reduction.
   |

| Table 8: Non-Hematologic Toxicity Management  |  |  |
|---|--|--|
| Event Terms   | CTCAE Grade                                  | Management Guidelines  |

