| Any other non-hematologic toxicity  | ≥ Grade 3                                    | 
Hold dosing until resolution to ≤ Grade 2 or baseline. Upon resolution, resume with one dose level reduction. Exceptions:
 
 
Grade 3 nausea, vomiting, diarrhea, or constipation that was not medically managed: appropriate medical management should be initiated, and study medication should be held until resolution to ≤ Grade 2 or baseline. Upon resolution, study medication may be resumed at the same dose level or with one dose level reduction at the treating investigator's discretion.
 
Asymptomatic laboratory abnormalities that resolve to ≤ Grade 2 or baseline within 48 hours of repletion or treatment: study medication should be held until resolution to Grade 2 and may be resumed at the same dose level or with one dose level reduction at the treating investigator's discretion. Treatment and resumption of study medication dosing may occur on the same day.
 
Asymptomatic laboratory abnormalities considered non-clinically significant: participants may continue dosing at the treating investigator's discretion.
 
 |
| 
 
At the treating investigator's discretion, participants experiencing intolerable grade 2 toxicities may hold and/or dose reduce LY3214996 and/or HCQ.
 
At the treating investigator's discretion, dose of LY3214996 and/or HCQ may be reduced by one dose level.
 
Please refer to Appendix C for rash management guidelines.
 
 |  |  |

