| ∞ : Cross-over participants do not need to re-screen but must provide re-consent prior to initiating cross-over treatment. First day of combination treatment will be considered C1D1 of cross-over.
See Section 5.1.4 .
¥ : Note: column relevant only for CRF builders.
a. Please refer to Section 5.2.1 .
b. A ± 3 day scheduling window is allowable to account for holidays, adverse weather, vacations, or any other scheduling issues.
c. A ± 7 day scheduling window is allowable to account for holidays, adverse weather, vacations, or any other scheduling issues.
d. Off treatment evaluation. Note: for IND trials, follow up visits or other contact are required in order to identify SAEs during the 30 days following the end of study treatment.
e. Heart rate, respiratory rate, temperature, blood pressure, and oxygen saturation; to be performed prior to study agent dosing.
f. Albumin, alkaline phosphatase, total bilirubin, bicarbonate, BUN, calcium, chloride, creatinine, glucose, potassium, total protein, SGOT [AST], SGPT [ALT], sodium, phosphorus, creatinine phosphokinase (CPK).
g. Serum pregnancy test only required for women of childbearing potential. Childbearing potential defined as any female who has experienced menarche and who has not undergone successful surgical sterilization (hysterectomy, bilateral tubal ligation or bilateral oophorectomy) or is not postmenopausal (defined as amenorrhea >12 consecutive months; or women with a documented plasma follicle-stimulating hormone level >35µU/mL).
h. EKG to be collected during screening, C1D8, on C1D15, C1D22, C2D1, and C3D1 at any time during the study visit, and as clinically indicated. Single EKG to be collected at each time point. QTc to be calculated using Bazett's formula.
i. Radiologic imaging of any disease-involved site.
j. A tumor biopsy is mandatory at baseline for all participants, and optional at the time of disease progression for all participants. Tumor biopsies to be collected as per Section 9.1 . A repeat screening tumor biopsy is not required for cross-over participants (i.e. participants are not required to have a biopsy prior to crossing-over).
k. Blood samples to be collected as per Section 9.2 .
l. To be performed by an ophthalmologist. Exam required during screening and on Cycle 3 Day 1 (± 7 day window). In addition, exam required if participant experiences new or worsening visual disturbances or suspected ocular toxicity while receiving trial treatment.
m. PK sample collection only required on participants enrolled to the Safety Lead-in Cohort and the first six evaluable participants enrolled to Arm 1 . Refer to Section 9.3 for details.
n. Adequate supply of the study agents should be dispensed to account for any pre-planned scheduling delays.
o. Following treatment discontinuation, participants will continue to be followed for survival status only for 6 months or until death, whichever occurs first. Survival status may be verified via medical record review, contact with care providers, or telephone contact with the patient. A ±14 day window is allowed for survival status verifications. |   |                                    |               |                            |                             |                             |                             |                             |                            |   |  |

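### The EKG required before Arm 2 participants cross over to HCQ has no QTc limit, so the 470 msec entry limit is not re-applied before their first HCQ dose

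*Combined protocol and SAP*

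**What the plan says.** Section 5.1.4 lists five criteria for cross-over from Arm 2 to the combination. Item 4 reads: "The participant must have a tumor imaging assessment and EKG prior to initiating cross-over treatment (within 28 days of the start of combination dosing". No acceptance value follows. Item 2 of the same list does carry a number, ECOG performance status of 1 or less.

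The only numeric QTc limit in the protocol is Section 3.1.10: a baseline QTcB of at most 470 "msec on screening EKG". It applies to every participant at entry.

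The Table 11 footnotes in Section 10 state: "Cross-over participants do not need to re-screen but must provide re-consent prior to initiating cross-over treatment". They add: "First day of combination treatment will be considered C1D1 of cross-over". Footnote h sets the EKG schedule on the combination: "EKG to be collected during screening, C1D8, on C1D15, C1D22, C2D1, and C3D1 at any time during the study visit, and as clinically indicated". On Arm 2 before cross-over, Table 12 schedules one EKG, at screening; any others are taken only if clinically indicated.

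Cross-over participants receive the dose then in use on Arm 1. Under Section 5.1.3.1 that is LY3214996 200 mg daily with HCQ 600 mg twice daily, unless the overall principal investigator has reduced it.

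**The concern.** The protocol treats QT prolongation as an HCQ hazard. Section 5.4.3 warns of ventricular arrhythmias and Torsades de Pointes, and Table 9 lists QTc prolongation as an expected HCQ toxicity. For an Arm 2 participant, cross-over is the first exposure to that hazard. The screening EKG was taken before any monotherapy, so the item 4 EKG is the only scheduled reading between entry and the first HCQ dose.

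As written, obtaining that EKG satisfies item 4 whatever it shows. At entry, a QTcB above 470 msec makes a participant ineligible, and Section 17.7.3 allows no eligibility exception without IRB approval. At cross-over, the same reading needs only the agreement of the treating investigator and the overall principal investigator. What is at stake is participant safety, not a trial estimate.

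**Working it through.** The plan states no figure to reproduce here. The check compares the sections and then works out some simple timings.

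**Does anything restore the 470 msec limit before the first HCQ dose?**

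| Provision | What it does | Numeric QTc limit before HCQ? |
|---|---|---|
| 3.1.10 | QTcB at or below 470 msec, on the screening EKG | Yes, but at trial entry only |
| Table 11 footnote | Waives re-screening at cross-over | No; 3.1.10 is not triggered again |
| 5.1.4 item 4 | EKG within 28 days before combination dosing | No |
| 5.1.4, opening text | Treating investigator's discretion and overall PI approval | No; judgement |
| 5.1.4, toxicity clause | Investigator checks for significant, unacceptable or irreversible toxicity | No; judgement |
| 5.1.4 item 1, pointing to 5.5 | No other discontinuation criterion met | No; 5.5 has no QTc criterion |
| 5.4.3 | Advises against QT-prolonging drugs; headed for participants receiving HCQ | No |
| Table 8 | Grade-based holds and reductions | No |
| Table 11 footnote h | EKGs on the combination | No; all follow the first dose |

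Table 8 needs a closer look. Section 6.3 limits it to toxicity judged at least possibly related "to HCQ and/or LY3214996 is detailed in the tables below". It has no QTc row. For other non-hematologic toxicity of Grade 3 or higher it requires a hold and then says: "Upon resolution, resume with one dose level reduction. Exceptions". For Grade 2 or lower the default is to leave dosing unchanged, although a footnote allows a hold or reduction for intolerable Grade 2 events. The rule works by grade and attribution and does not test a reading against 470 msec before HCQ starts.

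**When is the first scheduled EKG on HCQ?**

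- Inputs: the first combination day is C1D1, the first scheduled EKG is C1D8, and footnote b says of that visit that a ± "3 day scheduling window is allowable to account for holidays" and similar scheduling problems.
- Planned time from first dose: 8 − 1 = 7 days.
- With the window, the visit falls on Day 5 to Day 11: 5 − 1 = 4 days to 11 − 1 = 10 days.
- Scheduled twice-daily HCQ doses on the days before that visit: 7 × 2 = 14 as planned, 4 × 2 = 8 at the earliest, 10 × 2 = 20 at the latest. If that day's morning dose is taken before the EKG, each count rises by one, to 15 (9 to 21).

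**How old can the pre-HCQ EKG be?**

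- Arm 1: at most 14 days (Section 10 screening window), tested against 470 msec.
- Cross-over: at most 28 days (5.1.4 item 4), tested against no value.

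**How many participants?**

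Section 13.2 plans 20 participants in Arm 2, so 20 is the ceiling. The documents give no rate of QTcB above 470 msec at cross-over, so no expected count can be derived.

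**The case against.** The strongest reply is that the protocol does not overlook QT at cross-over. It requires an EKG and puts it before two physicians, either of whom may refuse. After entry it generally relies on judgement: Section 5.2.1 does not require C1D1 laboratory values to meet eligibility again, 5.1.4 re-applies no marrow, hepatic or renal limit, and Arm 1 participants already on HCQ have no numeric QTc stopping rule. Every cross-over candidate has also passed the 470 msec limit at entry, along with the exclusions for long QT syndrome (3.2.14) and uncontrolled illness including arrhythmia (3.2.10). EKGs remain available when clinically indicated.

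These points are fair and lower the likelihood of harm, but none supplies a limit before the first HCQ dose. The appeal to judgement is weakened by item 2, which re-applies the numeric ECOG limit at this very step, and by item 4, which asks for the EKG and omits the value to judge it by.

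Three further points stand as context. The C1D8 timing is the same for Arm 1, so it shows only that later EKGs cannot replace a check before dosing; it does not measure a gap specific to cross-over. The ceiling of 20 is well above any likely count, because a participant must progress radiologically, keep ECOG 0 or 1, avoid rapid progression, choose to cross over, be approved, and have a QTcB above 470 msec. An amendment also carries paperwork beyond the sentence itself.

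**Conclusion.** The concern holds. Followed as written, the protocol lets an Arm 2 participant with a pre-cross-over QTcB above 470 msec meet all five criteria and begin HCQ, on physician agreement alone. What is missing is a written limit; the EKG itself is required.

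The number exposed is at most 20 and may be small. QTc prolongation is not listed for LY3214996 alone, either among related events in 10% or more of patients (Table 1) or among the expected serious reactions in Section 7.1.2. The conclusion needs no assumption about that rate; it rests on reading the re-screening waiver as covering 3.1.10, which is its plain meaning. No efficacy conclusion changes: cross-over follows progression on Arm 2, and Section 13.3.2 leaves cross-over participants out of the primary analysis of the combination. This is a design choice that should be changed because the possible harm is serious and the remedy is cheap.

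**What to change.** Add to Section 5.1.4 item 4: *QTcB on this EKG must be at or below 470 msec.* Add to the Table 11 re-screening footnote: *except for the QTcB limit in Section 5.1.4 item 4.* Keep the 28-day window.

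The EKG is already required, so there is no new procedure or visit. The wording does not forbid a repeat EKG within the window, for example after a reversible cause has been corrected. The clinical cost is that a few participants may be unable to cross over. The administrative cost is a protocol amendment with IRB approval; under Section 17.2, participating institutions have 90 days from notification to approve and implement a non-life-threatening revision.

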##### 5.1.3.1 Arm 1 Treatment: LY3214996 + HCQ

If **Dose Level 0** was found tolerable, enrollment to **Arm 1** will initiate with LY3214996 at a dose of 400 mg PO daily and HCQ at 600 mg PO BID. Following accrual of six evaluable participants to **Arm 1**, enrollment to **Arm 1** will be paused for an assessment of safety of the increased dose of HCQ.

The safety assessment will occur after all six participants on **Arm 1** have completed at least one cycle of dosing with the combination. Participants must have received at least 75% of their assigned doses of LY3214996 and HCQ to be considered evaluable for this safety analysis, unless dosing was held or reduced due to toxicity. If one or more of the first six participants enrolled does not meet this parameter for a reason other than toxicity (e.g. rapid disease progression and subsequent removal), **Arm 1** will continue to accrue as many participants as needed to have six evaluable participants for safety assessment. **Participants will be replaced in**

***the randomized portion of the trial if they withdraw consent for participation before initiating protocol therapy or rapid disease progression limits their ability to receive any therapy per protocol.*** All participants accrued to the arm who start protocol treatment will be considered evaluable for efficacy endpoints, regardless of whether they meet criteria to be considered evaluable for assessment of safety of the increased dose of HCQ.

The overall principal investigator will review applicable adverse event data and determine if enrollment should continue with HCQ at the 600 mg dose level. At the discretion of the overall principal investigator, the dose level may be reduced for all participants remaining to be accrued to the arm.

If **Dose Level 0** was not tolerable, but **Dose Level -1** was tolerable, enrollment to **Arm 1** will be initiated with LY3214996 200 mg PO QD and HCQ600 mg PO BID. An interim safety assessment will still occur in this scenario. If **Dose Level -1** was also not tolerable, **Arm 1** will not move forward. The trial will proceed with enrollment to **Arm 2** only, evaluating LY3214996 as monotherapy.

**At the conclusion of the safety lead-in cohort, on March 26, 2021 findings demonstrated that Dose Level 0 was not tolerable, but Dose Level -1 was tolerable. Therefore, patients enrolling to the randomized two arm portion of the trial will receive:**

**Arm 1 LY3214996 200 mg QD and 600 mg HCQ BID and  

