#### 5.1.3.2 Arm 2 Treatment: LY3214996

Participants enrolled to **Arm 2** will receive treatment with LY3214996 at the recommended phase II dose of 400 mg PO once daily.

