## 6.2 Dose Modifications

Dose reductions may be made in accordance with the tables below. Once a participant's dose of HCQ or LY3214996 has been reduced, it may be re-escalated to the previous dose level if the toxicity has resolved to baseline or  $\leq$  Grade 1 with agreement from the overall principal investigator. If the toxicity recurs necessitating another dose reduction, the dose may not be re-escalated.

| Table 5: HCQ Dose Reductions |  |
|-------------------------------------|--|
| Original HCQ Dose (PO BID)   | HCQ Dose Reduction (PO BID)     |
| 600 mg                              | 1 st Reduction: 400 mg      |
|                                     | 2 nd Reduction: 200 mg      |
|                                     | 3 rd Reduction: Discontinue |
| 400 mg                              | 1 st Reduction: 200 mg      |
|                                     | 2 nd Reduction: Discontinue |
| 200 mg                              | Discontinue                            |

| Table 6: LY3214996 Dose Reductions |  |
|---|--|
| Original LY3214996 Dose (PO Daily) | LY3214996 Dose Reduction (PO Daily) |
| 400 mg                                    | 1 st Reduction: 200 mg          |
|   | 2 nd Reduction: 100 mg          |
|   | 3 rd Reduction: Discontinue     |
| 200 mg                                    | 1 st Reduction: 100 mg          |
|   | 2 nd Reduction: Discontinue     |

If attribution of the toxicity is known, dose reductions may occur independently of each other. For example, the dose of HCQ may be reduced while maintaining the dose of LY3214996. If toxicity attribution is unknown or the combination of study agents may contribute to the toxicity,

both agents must be dose reduced.

If attribution of the toxicity is known, discontinuation of study medications may also occur independently of each other with agreement from the overall principal investigator. For example, participants who cannot tolerate HCQ may be allowed to continue to receive LY3214996 if the overall principal investigator agrees. If toxicity attribution is unknown or the combination of study agents may contribute to the toxicity, the participant should be removed from protocol therapy.

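### Sections 5.1.4 and 6.2 conflict on the LY3214996 dose at cross-over for one narrow group: Arm 2 participants at 100 mg who are barred from re-escalation

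*Combined protocol and SAP*

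**What the plan says.** Under Section 5.1.4, Arm 2 participants with radiologic progression on monotherapy "will have the option to cross-over to receive treatment with the combination". The dose is then given in one unconditional sentence: "Participants who cross-over will receive LY3214996 and HCQ at the dose being administered to" Arm 1 participants. Five criteria and a general toxicity check precede cross-over, and none mentions dose history. The only dose ceiling stated there is for HCQ.

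The doses in force follow from the lead-in. Section 5.1.3.1 records that Arm 1 is "LY3214996 200 mg QD and 600 mg HCQ BID". Section 5.1.3.2 says that Arm 2 participants "will receive treatment with LY3214996 at the recommended phase II dose of 400 mg PO once daily".

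Section 6.2 governs individual dose changes. Table 6 takes a 400 mg starter to 200 mg, then 100 mg, then discontinuation. A reduced dose can be raised again: "it may be re-escalated to the previous dose level if the toxicity has resolved to baseline or" at most Grade 1, provided the overall principal investigator agrees. The next sentence limits this: "If the toxicity recurs necessitating another dose reduction, the dose may not be re-escalated". That limit carries no provision for the overall principal investigator to override it.

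Two other places bear on the point. The opening of Section 5.1 refers to Section 6 for dose modifications. A footnote to Table 11 says that cross-over participants re-consent without re-screening and that their cycle count restarts at C1D1.

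**The concern.** Section 5.1.4 fixes the LY3214996 dose at cross-over by arm, whatever the participant's own dose was on monotherapy. Section 6.2 fixes what an individual may receive by that person's toxicity history. Where the history has left someone below the Arm 1 dose with re-escalation barred, the first rule calls for an increase that the second forbids.

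The participants concerned have already had LY3214996 toxicity come back, and the increase would fall on the day they first take HCQ. An investigator who follows either section to the letter would depart from the other, and the documents do not say which departure is the deviation. It is also unclear how later reductions are counted, because the plan does not say whether the Arm 2 reduction history survives the restart at C1D1.

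**Working it through.** The plan states no figure on this point, so there is nothing to reproduce. The check lists every LY3214996 state that an Arm 2 participant can be in when cross-over is considered and compares it with the dose that Section 5.1.4 assigns.

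Inputs:
- Arm 2 starting dose: 400 mg once daily (Section 5.1.3.2).
- Levels below it: 200 mg, then 100 mg (Table 6).
- Re-escalation: one level up, if the toxicity has resolved and the overall principal investigator agrees; barred after a recurrence that needs another reduction (Section 6.2).
- Dose assigned at cross-over: 200 mg once daily (Section 5.1.4 with Section 5.1.3.1).

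| Dose on Arm 2 | Re-escalation barred? | Example of how it is reached | Change to 200 mg | Result |
|---|---|---|---|---|
| 400 mg | No | No reduction | Down | No conflict |
| 200 mg | No | 400 → 200 | None | No conflict |
| 200 mg | Yes | 400 → 200 → back to 400 → recurrence → 200 | None | No conflict |
| 100 mg | No | 400 → 200 → 100, the second step for a different toxicity | Up one level | Allowed by 6.2 if resolved and agreed |
| 100 mg | Yes | 400 → 200 → recurrence → 100 | Up one level | Conflict |

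One of the five states is in conflict. The size of the increase there is 200 / 100 = 2.0, a doubling.

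The result does not depend on how the bar is read. It comes straight after the permission to re-escalate, so it could be taken to apply only when toxicity recurs after a re-escalation. The barred 100 mg state can still be reached on that reading, by 400 → 200 → 100 → back to 200 → recurrence → 100.

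The result does depend on the Arm 1 dose. Had Dose Level 0 been tolerable, Arm 1 would have used LY3214996 400 mg, and barred participants at 200 mg would also have been in conflict. That did not happen.

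Carry-over of the history also makes a difference. If it carries over, a participant at 100 mg has used two steps of the 400 mg row in Table 6, and the next step listed is discontinuation. If the participant instead starts afresh in the 200 mg row, a step to 100 mg is still available. The documents support neither count over the other.

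**The case against.** The strongest reply is that there is no contradiction, only two rules at different levels. Section 5.1 refers to Section 6 for dose modifications, so the doses named under 5.1 can be read as assigned doses that Section 6 then limits for the individual. The Arm 2 dose of 400 mg is stated just as flatly, and nobody would say that it contradicts Table 6. This is a sensible reading and it softens the conflict. It does not remove it. The reference is a pointer with no statement of precedence, and the C1D1 restart leaves open whether a reduction made on Arm 2 still counts after cross-over.

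A second reply is that both rules can always be met, because cross-over is optional and such a participant need not cross over. That is correct. A reader might infer that the two sections can never both be followed, and the documents do not support that: they collide only if a barred participant at 100 mg does cross over. But the plan does not list this as a ground for withholding cross-over. The overall principal investigator's approval is for cross-over itself, and Section 5.1.4 does not extend it to the dose. The general toxicity check could be passed by someone whose toxicity settled at 100 mg.

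Three further inferences should be resisted:
- That every participant with a reduced dose is affected. Those at 200 mg are already on the Arm 1 dose, and an unbarred participant at 100 mg may move up one level under Section 6.2 on its conditions.
- That the lead-in showed the cross-over dose to be intolerable. The level found not tolerable was LY3214996 400 mg with HCQ 400 mg. Dose Level -1, LY3214996 200 mg with HCQ 400 mg, was tolerable. The lead-in did not test the HCQ 600 mg twice daily now used in Arm 1.
- That each site would apply its own rule. Every cross-over passes through the overall principal investigator, so decisions are central.

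**Conclusion.** The point holds in a narrow form. Sections 5.1.4 and 6.2 give incompatible instructions on LY3214996 for an Arm 2 participant who is at 100 mg, is barred from re-escalation after recurrent toxicity, and crosses over while the Arm 1 dose is 200 mg. For that participant the difference is a factor of two in the LY3214996 dose.

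How many people this covers cannot be derived. The documents give no rate of second reductions, recurrent toxicity or cross-over. The only bound is the 20 participants planned for Arm 2 (Section 13.2), and any smaller figure would be a guess. An affected participant must also have radiologic progression, ECOG status of at most 1, a passed toxicity check, re-consent and approval, so the group is likely to be small.

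The primary analysis of combination treatment is not affected: Section 13.3.2 leaves cross-over participants out of it. Section 5.1.4 likewise leaves them out of the six-participant Arm 1 safety review.

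The text is wrong as written, but the matter is minor. This rests on the doses stated in Section 5.1.3.1 remaining in force and on there being no precedence rule elsewhere in the document; none was found.

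**What to change.** Reconcile Sections 5.1.4 and 6.2. The text should settle two things:
- Which section governs the LY3214996 dose at cross-over for a participant whose dose is below the Arm 1 dose, and in particular for one barred from re-escalation.
- Whether the Arm 2 reduction history carries over when the cycle count restarts at C1D1, and which row of Table 6 then applies.

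The content of both is a clinical decision for the sponsor, and no dose or rule is proposed here. The cost is a sentence or two in Section 5.1.4 and a cross-reference in Section 6.2, made by amendment. No participants, visits or procedures are added, and the sample size and primary analysis stay as they are.
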